An open label pilot trial of guselkumab in the treatment of adults with Pityriasis Rubra Pilaris (PRP)

Protocol Version Number:	1.1						
Protocol Version Date:	23 January 2019						
Investigational Product:	Guselkumab						
IND/IDE Status:	Exempt						
Principal Investigator	[name], PhD						
	Department of Dermatology						
	Oregon Health & Science University, Center for Health and Healing						
	[name]						
	[name]						
	[contact]						
	[contact]						
	Email: [contact]						
Sponsor:	Oregon Health & Science University						
Funding Source:	Janssen Scientific Affairs						
Trial Configuration	Single center, open label, interventional, investigator-initiated trial						

CLINICAL PROTOCOL SYNOPSIS

Title	An open label pilot trial of guselkumab in the treatment of adults with pityriasis rubra pilaris (PRP)					
Principal Investigator	[name], PhD					
Objectives	To determine whether guselkumab provides clinical improvement for subjects with PRP who are candidates for systemic therapy					
Trial Configuration	Single center, open label, interventional, investigator-initiated trial					
Setting	The trial will recruit 15 adults with moderate-to-severe (defined involved body surface area (BSA) ≥ 10%) PRP through dermatolog offices, recruitment letters, and advertisement.					
	Study visits will occur at Screening, weeks 0, 4, 8, 12, 20, 24, and 36. Study visits at weeks 0, 4, and 24 will be required in-person; the remaining visits optionally will be performed via secure video- conferencing using the OHSU Nexus (Cisco Meeting) app, between the investigator and the subject, as well as a REDCap survey sent via email.					
Sample Size Estimate	With measurement of the mean paired difference in PASI score before and after treatment of a minimum of 10 subjects, we would have 80% power at the 0.05 level to detect a mean within-subject change of 8- points when the standard deviation is 8-points. Due to the uncertainty inherent with a pilot study, the goal number of subjects with PRP who will be recruited for the study is 15.					
Number of Participants	15 subjects with moderate-to-severe PRP					
Eligibility Criteria	 Willingness to comply with study procedures/requirements. Capable of giving informed consent. Diagnosis of PRP by clinical assessment and biopsy. Male age 18-99, willing to use a reliable form of birth control if sexually active with a woman who is able to become pregnant. Female age 18-99; either of non-childbearing potential or of childbearing potential who test negative for pregnancy and agree to use a reliable method of birth control or remain abstinent during the study and for at least 12 weeks following the last dose of guselkumab. Involved BSA ≥ 10% at baseline (moderate-to-severe disease). Are a candidate for phototherapy and/or systemic therapy. Willingness to travel to OHSU for all study visits, or willing/able to participate in remote videoconferencing visits with access to a computer with internet and webcam capabilities. 					
	 Exclusion criteria Known malignancy or lymphoproliferative disease (except treated basal cell skin cancer, treated squamous cell skin cancer, or treated cervical carcinoma in situ) for at least 5 years. Active, untreated, acute or chronic infection, or 					

 immunocompromised to an extent that such that participation in the study would pose an unacceptable risk to the subject. Positive for human immunodeficiency virus, hepatitis B virus, or
 Positive for human infinitionodenciency virus, nepatitis B virus, or hepatitis C virus.
 Have latent or active untreated tuberculosis (TB), a positive QuantiFERON-TB Gold test result, signs or symptoms of active TB on medical history or physical examination, or close contact with a person with active TB who have not undergone evaluation or treatment for TB. Those who are currently undergoing treatment or who have documented completed treatment for active or latent TB without re-exposures will not be excluded.
 Previous treatment with any agent that targets the interleukin 23 p19 subunit specifically.
 Systemic treatment with prednisone in the last 2 weeks, or other systemic therapies or phototherapy for PRP within the past 4 weeks or 5 half-lives prior to baseline, whichever is longer. For biologic therapies, the specific washout periods used will be: etanercept <28 days; infliximab, adalimumab, ixekizumab, or alefacept <60 days; golimumab <90 days; secukinumab <5 months; ustekinumab <8 months; rituximab or efalizumab <12 months.
 Have a known allergy or hypersensitivity to any biologic
therapy that would pose an unacceptable risk to the subject if participating in this study.
 Have or intend to have a live vaccine within 3 months prior to baseline or 12 months prior to baseline in the case of the BCG vaccine, or any live vaccine during the course of study or within 3 months after the last administration of study drug.
 Had any major surgery within 8 weeks prior to baseline or will require major surgery during the study, that in the opinion of the investigator would pose an unacceptable risk to the subject.
 Presence of significant uncontrolled cerebrovascular, respiratory, hepatic, renal, gastrointestinal, endocrine, hematologic, neurologic, or neuropsychiatric disorders, or abnormal laboratory screening values that, in the opinion of the investigator, pose an unacceptable risk to the subject if participating in the study or of interfering with the interpretation of the data.
 Have clinical laboratory test results at screening that are outside the normal reference range of the population and are considered clinically significant, or have any of the following specific abnormalities: Neutrophil count <1500 cells/µL, white blood cell count <3500 cells/µL, platelet count <100,000 cells/µL, AST or ALT or alkaline phosphatase > 2 times the upper limit of normal, hemoglobin <10 g/dL, serum creatinine >1.5 mg/dL. A single retest of laboratory values is permitted if one or more values is out of range.
 Women who are lactating or breastfeeding.
 Have any other condition that precludes the subject from
following and completing the protocol, in the opinion of the investigator.
 Are investigator site personnel directly affiliated with this study and/or their immediate families (spouse, parent, child, or

	 sibling). Are currently enrolled in, or discontinued from a clinical trial involving an investigational product or non-approved use of a drug or device within the last 4 weeks or a period of at least 5 half-lives of the last administration of the drug, whichever is longer, or concurrently enrolled in any other type of medical research judged not to be scientifically or medically compatible with this study.
Description of Interventions	Subjects with PRP will be treated with guselkumab for 20 weeks using the FDA-approved dosing schedule for psoriasis (100 mg subcutaneous injection at weeks 0, 4, 12, and 20).
Duration of Study	The duration of the study will be 36 weeks
Outcome Measures	The primary outcome will be the mean change from baseline PASI at week-24 after treatment with guselkumab. Secondary and mechanistic outcomes include measurement of
	improvement in body surface area, nail involvement, quality of life, itch, pain; time to improvement by 50%; sustained remission at 36 weeks; and correlation of improvement with germline genetic mutations and cutaneous and serum cytokine expression.
Statistical Methods	Mean improvement from baseline PASI at week-24 will be analyzed for statistical significance using a paired, two-tailed Student's t-test.

Table of Contents

CLINICAL PROTOCOL SYNOPSIS	2
ABBREVIATIONS	7
1. BACKGROUND	8
1.1. OVERVIEW OF PITYRIASIS RUBRA PILARIS (PRP) AND GUSELKUMAB	8
1.2. Hypothesis	8
2. OBJECTIVES	8
2.1. PRIMARY OBJECTIVE	8
2.2. SECONDARY OBJECTIVES	9
2.3. EXPLORATORY OBJECTIVES	9
3. STUDY DESIGN AND ENDPOINTS	9
3.1. Study Design Overview	9
3.2. Study Endpoints	9

10.5. PROTOCOL REVIEW	
10.6. Changes to Protocol	32
11. PUBLICATION AND DISSEMINATION POLICY	32
12. REFERENCES	33

ABBREVIATIONS

AE	Adverse Event							
BSA	Body Surface Area							
CARD14	CAspase Recruitment Domain family, member 14							
CBC	Complete Blood Count							
CMP	Comprehensive Metabolic Panel							
CRF	Case Report Form							
DLQI	Dermatology Life Quality Index							
eCRF	Electronic Case Report Form							
EDC	Electronic Data Capture							
HBV	Hepatitis B Virus							
HCV	Hepatitis C Virus							
HIV	Human Immunodeficiency Virus							
IL23	Interleukin-23							
IND	Investigational New Drug							
iPRPASI	Individual PRP Area and Severity Index							
NAPSI	Nail Psoriasis Severity Index							
NRS	Numeric Rating Scale							
OHRP	Office for Human Research Protections							
OHSU	Oregon Health and Science University							
PCQ	Product Quality Complaint							
PASI	Psoriasis Area and Severity Index							
PGA	Physician's Global Assessment							
PI	Principal Investigator							
PPPGA	Palmoplantar Physician's Global Assessment							
PRP	Pityriasis Rubra Pilaris							
SAE	Serious Adverse Event							
SC	Subcutaneous							
SOAP	Subjective, Objective, Assessment, Plan							
Th17	T Helper 17 cell							
UP	Unanticipated Problem							

1. BACKGROUND

1.1. Overview of Pityriasis Rubra Pilaris (PRP) and Guselkumab

Pityriasis rubra pilaris (PRP) is a rare and poorly understood severe inflammatory cutaneous disease characterized by widespread (often full-body) erythematous plaques, skin flaking and ichthyosis, painful thickening and cracking of the palms and soles, hair loss, crumbling nails, and severe skin pruritus and burning. The most common type of PRP affects otherwise-healthy adults and may be explosive in onset. Although PRP does not affect internal organs and no quality-of-life impact studies have been published, the high degree of morbidity is perhaps best illustrated by the following colorful quotes from members of a PRP Facebook support group (with >800 members):

"All I want is normal skin... for my eyes to stop watering constantly, to take off my clothes one time and not be shrouded by a cloud of dusty skin flakes..."

"My husband can barely walk or use his hands."

"My scalp is like the Sahara Desert experiencing the dust storm of the century."

"I want my life back!!! Please."

Not surprisingly, one study showed over half of patients with PRP reporting depression (1).

While the pathogenesis of PRP is poorly understood, similarities with inflammatory pathways in psoriasis have been reported. The major effector cells present in psoriatic lesions are Th17 cells, and a recent case report showed similar overexpression of cytokines in the Th17 pathway in cutaneous lesions of PRP, including the primary effector cytokines IL-23, IL-22, and IL-17 (2). Additionally, familial cases of both psoriasis and PRP have been associated with germline gain-of-function mutations in the caspase recruitment domain family, member 14 (CARD14) gene (*3*, *4*), and cutaneous overexpression of CARD14 was observed in cases of sporadic PRP (5). CARD14 overexpression *in vitro* has also been shown to induce excess IL-23 (6).

Guselkumab is a high affinity, humanized IgG1 lambda monoclonal antibody that selectively binds the p19 subunit of IL-23. Two phase III studies of guselkumab in the treatment of psoriasis showed excellent safety and efficacy, with "clear" or "almost clear" skin ratings in 84-85% of patients at week-16 (*7, 8*).

There is no FDA-approved therapy for PRP, not a single published systematic therapeutic clinical trial, and no established guidelines for measuring disease severity. Commonly prescribed systemic medications include acitretin and methotrexate, but these have treatment failure rates of over 40% (1) and can be limited by side effects. Tumor necrosis factor inhibitors have been used for PRP but have even higher failure rates (1). While there are no published reports of IL-23p19 subunit-targeted therapy in PRP, there are case reports and case series of the use of IL-12/IL-23p40 subunit inhibition for PRP in over twenty patients (2, 9-23) with 90% of these showing marked improvement, often only 4 weeks after a single subcutaneous injection. For these reasons, guselkumab is proposed as a therapeutic intervention with potential for improving the lives of PRP patients.

1.2. Hypothesis

Treatment of subjects who have moderate-to-severe PRP with guselkumab will lead to clinically significant improvement in subjective and objective measures of disease severity.

2. OBJECTIVES

2.1. Primary Objective

Determine whether guselkumab provides clinical improvement for subjects with PRP who are candidates for systemic therapy

2.2. Secondary Objectives

Use systematic measurement tools to associate the severity of cutaneous involvement of PRP with quality of life measures, before and after therapy with guselkumab

2.3. Exploratory Objectives

Explore the mechanisms by which guselkumab alters the cutaneous and systemic inflammatory milieu in PRP

3. STUDY DESIGN AND ENDPOINTS

3.1. Study Design Overview

This will be an investigator-initiated, open-label pilot study of 15 subjects with moderate-to-severe PRP treated with guselkumab at the FDA-approved dosing for psoriasis for 20 weeks, examining the primary efficacy endpoint of mean decrease in PASI score at week-24. Sustained remission will be assessed at week-36. Biopsies will be obtained before the first injection and at week-4 and week-24. Blood tests will be performed for screening and safety and measuring levels of inflammation at Screening, week-0, week-4, and week-24. The study schedule is outlined in Section 5.4., Table 1.

3.2. Study Endpoints

3.2.1. Primary Endpoint

Mean change from baseline PASI at week-24 after treatment with guselkumab.

The Psoriasis Severity Index (PASI) is a well-validated tool for measuring psoriasis, based on redness, thickness, scale, and body surface area assessed by the investigator, with a maximum score of 72 points. This is expected to be a useful tool for PRP, since PRP is characterized by widespread bright red erythema and scale, and is often initially misdiagnosed as severe psoriasis. The mean thickness score is expected to be lower in PRP than psoriasis but the mean body surface area (BSA) is expected to be higher than psoriasis.

3.2.2. Secondary Endpoints Assessed by Investigator

- Time to improvement by 50% in the PASI score (PASI 50)
- Mean reduction in body surface area (BSA) at week-24. BSA is collected as part of the PASI assessment tool.
- Proportion of subjects achieving a Physician's Global Assessment (PGA) of 0 or 1 at week-24
- Proportion of subjects achieving a Palmoplantar Physician's Global Assessment (PPPGA) of 0 or 1 at week-24. Palmoplantar disease will be assessed separately from overall disease since it has high morbidity and may respond differently to therapy.
- Mean percentage improvement in nail involvement measured by Nail Psoriasis Severity Index (NAPSI) at week-24. The Nail Psoriasis Severity Index (NAPSI) (24) will be used for evaluating the fingernails and toenails of subjects with PRP. This is expected to be useful tool because nails in PRP have many overlapping features with psoriasis including nail plate crumbling, splinter hemorrhages, nail oil drop (yellow-brown) discoloration, and nail bed hyperkeratosis, although PRP nails are less likely to have onycholysis and red spots in the lunula (25).

3.2.3. Secondary Endpoints Assessed by Subject

 Proportion of subjects achieving a 4-point improvement in quality of life measured by the Dermatology Life Quality Index (DLQI) at week-24, proportion of patients achieving a DLQI of 0 or 1 at week-24, and mean improvement in DLQI score at week-24. The DLQI (26) is a validated tool for inflammatory skin conditions. It is a 10-question survey, scored 0 – 30 points. For inflammatory skin conditions, a 4-point change in DLQI score is considered clinically important (27).

- Mean percentage in improvement in Psoriasis Symptoms and Signs Diary (PSSD) at week-24, and proportion of patients achieving a PSSD of zero at week-24. The PSSD is an 11-question 0 – 10-point numeric rating scale (NRS) patient-reported outcome measure assessing itch, dryness, cracking, skin tightness, scaling, shedding or flaking, bleeding, burning, stinging, and pain over the last 24 hours and 7 days respectively (28).
- Mean change from baseline individual PRP Area and Severity Index (iPRPASI) at week-24 after treatment with guselkumab, and correlation of subject-assessed iPRPASI scores with investigator-assessed PASI scores. The IPRPASI is a novel subject self-assessment score of disease involvement and severity, based on a previously published similar tool validated for psoriasis (29).
- Sustained remission at week-36, 16 weeks after the last guselkumab dose, as measured by the mean change in PASI from week-24 to week-36. Sporadic PRP is often a self-limited disease, resolving spontaneously after an average of 3-6 years. Other immunomodulatory medications have induced sustained remission of PRP (22), so there is a potential that treatment may "reset" the immune response and lead to long-term improvement in the disease, especially in subjects without genetic mutations. Subjects will be treated with guselkumab as per the FDA-approved psoriasis treatment guidelines, and therapy will be stopped after the 20-week dose. Subjects will be monitored at 24 weeks (primary study endpoint) and then at 36 weeks to assess for sustained remission versus relapse.

3.2.4. Exploratory/Mechanistic Endpoints

- Treatment response, as measured by PASI 50, stratified by the presence or absence of germline CARD14 mutations. Genetic CARD14 gain-of-function mutations were identified in 3 families with familial PRP as well as 12.5% of individuals with sporadic PRP (3). Genetic CARD14 mutations will be measured in study subjects and associated with treatment response to guselkumab. Additionally, de-identified samples will be stored indefinitely for future analysis of genes associated with PRP.
- Normalization of CARD14 epithelial expression at week-24. Despite the fact that not all patients with PRP have genetic CARD14 mutations, immunohistochemical staining of CARD14 in 6 of 6 biopsies from sporadic cases of PRP without germline genetic mutations showed increased expression of CARD14 in the keratinocyte spinous and granular layers of the epidermis (2). CARD14 is thought to act in a synergistic manner with IL-17, activating the transcription factor NF-kB. NF-kB activation was shown *in vitro* to stimulate IL-36gamma, which may induce an amplifying feedback loop from IL-23 to IL-17 and back again (6). Cutaneous biopsies will be obtained from subjects before and 24 weeks after treatment with guselkumab. Inhibition of IL-17 by guselkumab is expected to lead to normalization of CARD14 expression by keratinocytes.
- Normalization of cutaneous gene expression at weeks 4 and 24. Upregulation of Th17 cytokines (IL-17A, IL-17F, IL-22) and pro-inflammatory innate cytokines (TNF, IL-6, IL-12, IL-23, IL-1beta) compared to normal skin were observed in lesional skin from 3 subjects with PRP (5). In order to better understand the inflammatory pathways involved in PRP, lesional and non-lesional biopsies will be obtained from subjects at week-0 prior to the first dose of guselkumab, week-4, and week-24. Cutaneous gene expression of the epidermis and dermis will be analyzed by RNA Sequencing (RNA-Seq and therapeutic response to guselkumab is expected to correlate with normalization of epidermal cytokine levels. De-identified tissue samples will be stored indefinitely for analysis.
- Change in serum cytokine levels at weeks 4 and 24. Serum levels of multiple cytokines have been shown to correlate with disease activity in patients with psoriasis (*30*) but these have not been investigated in patients with PRP. Serum cytokine levels before and after treatment with guselkumab will be analyzed by multiplexed bead-based immunoassay.

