7. STATISTICAL CONSIDERATIONS

7.1. Sample Size Computation and Power Analysis

This is a pilot study with no published baseline data; thus a power analysis was performed with the following rough assumptions. With measurement of the mean paired difference in PASI score before and after treatment of a minimum of 10 subjects, we would have 80% power at the 0.05 level to detect a mean within-subject change of 8-points when the standard deviation is 8-points. Due to the uncertainty inherent with a pilot study, the goal number of subjects with PRP who will be recruited for the study is 15.

				Mean Change	Standard
Power (1-ß)	Sample Size	а	ß	in PASI	Deviation
0.9998	10	0.05	0.0002	-8	4
0.9940	10	0.05	0.0060	-8	5
0.9621	10	0.05	0.0379	-8	6
0.8942	10	0.05	0.1058	-8	7
0.8031	10	0.05	0.1969	-8	8
0.9873	10	0.05	0.0127	-6	4
0.9203	10	0.05	0.0797	-6	5
0.8031	10	0.05	0.1969	-6	6
0.6755	10	0.05	0.3245	-6	7
0.5620	10	0.05	0.4380	-6	8

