7.2.3. Exploratory Endpoint Analyses

- Sustained remission at week-36, measured by the mean change in PASI score from week-24 to week-36, will be analyzed for statistical significance using a paired, two-tailed Student's t-test.
- Treatment response, as measured by PASI 50, will be stratified by CARD14 germline mutations. The proportion of subjects with a PASI 50 response with and without CARD14 mutations will be reported and compared for statistical significance using an unpaired, two-tailed Student's t-test.
- Epithelial expression of CARD14 will be assessed qualitatively by a trained dermatopathologist who is blinded to the biopsy collection time (before or after therapy).
- The gene expression level from the tissue biopsy, before, 4 weeks, and 24 weeks after treatment, will be analyzed for statistical significance using a pared, two-tailed Student's t-test and also compared with normal and psoriatic skin using a two-tailed, two-sample Student's t-test with unequal variance adjusted for multiple comparisons.
- The cytokine level from serum before, 4 weeks, and 24 weeks after treatment, will be analyzed for statistical significance using a pared, two-tailed Student's t-test and also compared with normal and psoriatic serum using a two-tailed, two-sample Student's t-test with unequal variance adjusted for multiple comparisons.

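### Normalization of cutaneous gene expression is an exploratory endpoint, but no planned analysis measures how close treated skin is to normal, and a non-significant difference from normal could be misread as normalization

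*Combined protocol and SAP*

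**What the plan says.** Section 3.2.4 names the endpoint as "Normalization of cutaneous gene expression at weeks 4 and 24". It lists eight cytokines previously found raised in PRP lesions, plans RNA sequencing of lesional and non-lesional biopsies, and expects clinical response to go with normalized epidermal cytokine levels. It gives no reference range, margin or decision rule.

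Section 7.2.3 supplies two analyses. First, "The gene expression level from the tissue biopsy, before, 4 weeks, and 24 weeks after treatment, will be analyzed for statistical significance", by a paired two-sided t-test. Second, expression is "also compared with normal and psoriatic skin using a two-tailed, two-sample Student's t-test with unequal variance adjusted for multiple comparisons". This is the only planned comparison with normal skin. The number and source of normal samples, the number of genes tested and the adjustment method are not given. Non-lesional skin is collected as a control at week 0 where available (5.1.4), but no analysis in 7.2.3 mentions it.

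**The concern.** The endpoint asks whether expression has arrived at normal. The paired test asks whether it has moved, and a significant fall is compatible with a large remaining abnormality. The two-sample test asks whether a difference from normal can be shown. Its null hypothesis is no difference, so failing to reject it says little when samples are few.

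Multiplicity adjustment guards against false claims of difference. If the claim of interest is sameness, it works the other way: a stricter adjustment leaves more genes not significantly different from normal. With no criterion defined, a mechanistic statement that guselkumab normalized the skin could rest on low power.

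**Working it through.** **The plan's own figure.** The only power calculation concerns PASI: "80% power at the 0.05 level to detect a mean within-subject change of 8- points when the standard deviation is 8-points", with 10 subjects. For a paired t-test the noncentrality is 8/(8/√10) = 3.162 with 9 df and a two-sided critical value of 2.262. Power is 0.8031, which matches the table in 7.1. No corresponding figure is given for gene expression.

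**Inputs for the comparison with normal skin**
- Treated samples: 15 ("the goal number of subjects with PRP who will be recruited for the study is 15") or 10 ("after treatment of a minimum of 10 subjects"), both from 7.1.
- Normal samples: not stated; assumed 5, 10, 15 or 30.
- Number of tests m: not stated; 1, the 8 cytokines named in 3.2.4, or an assumed 20,000 genes.
- Adjustment: not stated; none, Benjamini-Hochberg or Bonferroni.
- True residual difference d: assumed, in SD units, with equal SDs in both groups.

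**Formula.** With k = √(1/n₁ + 1/n₂), the unequal-variance t statistic is approximately noncentral t with noncentrality d/k. The chance of a non-significant result is P(|T| ≤ c), where c is the two-sided critical value at 0.05/m. The smallest observed difference that reaches significance is c × k.

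**Worked case: 15 v 15, d = 1.** k = √(2/15) = 0.3651, noncentrality = 1/0.3651 = 2.739, df = 28.
- m = 1: c = 2.048, threshold 2.048 × 0.3651 = 0.75 SD, non-significant 25%.
- m = 8 (0.05/8 = 0.00625): c = 2.957, threshold 1.08 SD, non-significant 57%.
- m = 20,000: c = 5.884, threshold 2.15 SD, non-significant 99%.

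**Chance that a residual 1-SD difference is non-significant**

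| PRP v normal | Unadjusted | Benjamini-Hochberg, 8 | Bonferroni, 8 | Bonferroni, 20,000 |
|---|---|---|---|---|
| 15 v 15 | 25% | 30% | 57% | 99% |
| 10 v 10 | 44% | 58% | 77% | 99.9% |
| 15 v 10 | 36% | not run | 70% | >99% |
| 15 v 5 | 61% | not run | 90% | about 100% |
| 15 v 30 | 14% | not run | 41% | 98% |

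The Benjamini-Hochberg figures are simulated with all eight cytokines 1 SD off and independent. Simulation also agrees with the formula for the unadjusted and Bonferroni columns at 15 v 15 and 10 v 10.

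**Other residuals, Bonferroni over 8.** At 15 v 15 the chance of non-significance is 93% for 0.5 SD, 14% for 1.5 SD and 0.9% for 2 SD. At 10 v 10 a 2-SD residual is missed 10% of the time.

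**Would a formal equivalence test do better?** Take two one-sided tests with an assumed margin of 1 SD. At 15 v 15 and one-sided 0.05, a gene exactly 1 SD off is declared normal 5% of the time, against 25% if unadjusted non-significance is read as normal. But a truly normal gene is recognized only 69% of the time (14% at 0.05/8). At 10 v 10 it is 39% (2% at 0.05/8).

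**The case against.** A reader might infer that the plan will report every gene with a non-significant difference as normalized. The documents do not say so; no rule of that kind appears. What stands is that no criterion exists, so the misreading is open.

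The two-sample clause may have another purpose. It covers psoriatic as well as normal skin, and 7.2.3 repeats it for serum cytokines, where the endpoint is change and not normalization. It can be read as describing PRP against other skin, for which a difference test is suitable. That reading is fair, but it leaves the normalization endpoint with only the paired test, which cannot show arrival at normal.

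A reader might also infer that a clearly abnormal gene would pass as normal. At 15 v 15 and eight tests, a 2-SD residual is missed only about 1% of the time, and the documents give no lesional-to-normal difference in SD units to show that 1 SD is a clear abnormality. The 99% figure needs Bonferroni over an assumed 20,000 genes, and Bonferroni is not named in the plan.

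The argument does not extend to "Normalization of CARD14 epithelial expression at week-24". That endpoint is read qualitatively by a dermatopathologist blinded to collection time, with no t-test and no adjustment.

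Finally, the share of the gap closed is unstable when the starting gap is small. With a true week-0 gap of 1 SD and 15 v 15, the 95% interval for the gap includes zero about 25% of the time. This stands, and it limits where the ratio should be reported.

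**Conclusion.** The point holds in a limited form. Section 3.2.4 sets normalization as an endpoint, and 7.2.3 contains no analysis that estimates closeness to normal. Under the assumptions shown, a residual 1-SD difference is non-significant between 25% (15 v 15, unadjusted) and 77% (10 v 10, Bonferroni over eight) of the time. Fewer normal samples or a genome-wide Bonferroni family make it worse; 30 normal samples make it better. The sizes depend on unstated design details, but the direction does not: fewer samples or stricter adjustment always give more apparent normalization.

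The endpoint is exploratory in an open-label pilot. The risk is a misleading mechanistic statement; the primary PASI result, the sample size and safety decisions are not touched. This is a cheap improvement.

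**What to change.** In 7.2.3, for cytokines named in advance (the eight in 3.2.4 would serve) or a pathway score, on the log scale:
- Report the week-4 and week-24 difference from normal skin with a 95% CI.
- For markers whose week-0 gap from normal is clearly different from zero, report the share of that gap closed, (week 0 − week t)/(week 0 − normal) for t = 4 and 24, with a 95% CI.
- State that a non-significant difference from normal is not evidence of normalization.
- State the number and source of normal samples, the number of genes tested and the adjustment method.

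A formal equivalence margin is optional, because power for it is low at 10 to 15 subjects. At 15 v 15 the unadjusted 95% CI for the difference has a half-width of about 0.75 SD (0.94 SD at 10 v 10), so the interval will show the uncertainty that a non-significant p-value hides.

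Cost: revised SAP wording and slightly more analysis, with no new visits or biopsies. The source of the normal samples must be settled, but the existing comparison needs that too. The downside is that fewer markers can be described as normalized.
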